8.7. Data Analysis

Detailed methodology for summary and statistical analyses of data collected in this study will be documented in a Statistical Analysis Plan (SAP), which will be dated, filed and maintained by the sponsor. The SAP may modify the plans outlined in the protocol; any major modifications of primary endpoint definitions or their analyses would be reflected in a protocol amendment.

All analyses are to be descriptive and so all methods to be used will reflect this descriptive nature. The specific method that will be used depends on type of variable being analysed and those methods are:

- Categorical variables – will be described using:
 - Number of observations (n);
 - Number and percent (%) within each category;
 - Number of missing observations.
- Numeric variables – will be described using:
 - Number of observations (n);
 - Mean and Standard deviation;
 - Minimum, Maximum, Median and 1st and 3rd Quartiles;
 - Number of missing observations.
- Time to event – will be described using:
 - A Kaplan-Meier chart that will visually estimate the distribution of times to some events, eg, progression, and will take into account those patients for which the event has not as yet occurred;
 - 1-yr and 2-yr rates, median or some more appropriate percentiles if the median time is not reached in the sample.

The analyses will be conducted (using the methods above) in a number of phases, as already detailed in the study design section.

1. Non EU countries – all variables (as shown in [Section 8.3](#)) will be described.

2. EU countries – selected variables (all shown in [Section 8.3](#) excluding clinical outcomes) will be described.
3. EU countries - all variables will be described.

Missing data will be excluded on a case by case basis and will not be imputed. This will mean that each table will not necessarily be based on the same number of patients.

Subgroup Analysis

Exploratory stratifications will be conducted to explore differences between line of therapy, demographics, treatments, clinical characteristics, baseline co-morbidities or ‘responders’ and ‘non-responders’ to treatment, however these will be only descriptive in nature. Responders and non-responders will be defined according to the best recorded response to palbociclib treatment.

Sample size permitting, additional stratifications may include:

- Insurance type.
- Eastern Cooperative Oncology Group (ECOG) Performance status.
- Age.
- Menopausal status.
- De novo vs. recurrent disease.

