- Agrees to participate in the study and complete the CRFs.

¹ Breast surgeons/general surgeons/gastro-surgeons may also be included as relevant treaters in Japan.

Patient inclusion criteria

- ≥ 18 years old;
- HR+/HER- breast cancer diagnosis with confirmed metastatic or advanced disease;
- Received palbociclib plus letrozole/aromatase inhibitor or palbociclib plus fulvestrant in line with the licenced indication(s);
- No prior or current enrolment in an interventional clinical trial for ABC/MBC;
- Minimum of three months of follow up data since palbociclib with fulvestrant initiation, or minimum of six months of follow up data since palbociclib with letrozole/aromatase inhibitor initiation (core medical record review);
- Minimum of three months of follow up data since palbociclib initiation (German interim medical record review only);
- Inoperable or recurrent breast cancer (Japan only).

In order to ensure that sufficient data is captured for each indication, indication soft quotas will be enforced. This will be determined on a country by country basis.

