4. ANALYSIS SETS/POPULATIONS

4.1. Full Analysis Set

Only patients who meet the completed inclusion and exclusion criteria described in Section 3.0 and for whom a core medical record review was conducted will be included in the full analysis set (FAS).

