- Line of therapy that palbociclib is received (T);
- Treatments received in the line of therapy prior to palbociclib (T-1);
- Treatments received in the line of therapy post palbociclib (T+1).

Palbociclib dosing characteristics**To be abstracted directly from the medical records:**

- Palbociclib starting dose;
- Reasons for starting at a dose lower than 125 mg/day;
- Number of palbociclib dose changes;
- Details of each dose change (eg, dose increase, dose decrease, dose interruption, cycle delay);
- Date of dose change;
- Reason for dose change (eg, side effects/toxicity, lack of response);
- Status of combination partner therapy at dose change (eg, if continued or stopped).

To be derived

- Time from palbociclib initiation to first dose change;
- Duration of dose interruption;
- Duration of cycle delays.

Supportive therapies received during palbociclib treatment**To be abstracted directly from the medical records:**

- Supportive therapies received during palbociclib treatment.

Clinical Outcomes**To be abstracted directly from the medical records:**

- Initial response recorded;
- Time from palbociclib initiation to initial response;
- Frequency with which response to palbociclib was assessed;
- Proportion with complete response;
- Proportion with complete response defined by radiological evidence;
- Proportion with partial response defined by radiological evidence;
- Time from palbociclib initiation to complete response;
- Proportion with partial response;
- Time from palbociclib initiation to partial response.

To be derived

- Objective response rate defined as the proportion of patients achieving complete or partial response on palbociclib;
- Clinical benefit rate defined as the proportion of patients achieving complete or partial response, or stable disease ≥ 24 weeks on palbociclib. Stable disease will be defined as no evidence of complete or partial response, and no progression on palbociclib therapy for 24 weeks or greater;
- Proportion with stable disease ≥ 24 weeks on palbociclib;

█ [REDACTED]

- Progression free survival (if applicable) defined as the time from the start of palbociclib to the first subsequent progression or death;
- Time to death, defined as the time from the start of palbociclib to death;

█ [REDACTED]

- Progression free at 3, 6, 12, 18, 24 months defined as the proportion of patients who have no documented progression at defined time points;

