7.2. Statistical Methods

Based on the descriptive nature of the study, all study measures will be summarized descriptively through the tabular and graphical display of mean values, standard deviations, and ranges for continuous/numeric variables of interest. For categorical variables, frequency distributions (n, %) will be displayed. Missing and unknown categories for each variable also will be presented. Percentages will be calculated excluding missing values. All endpoints will be calculated for the overall population and by the stratification variables listed in [Section 4.3](#) (sample sizes permitting).

To show how one treatment line moves to the next, adjacent treatment combinations will be cross-tabulated (showing frequencies), eg, treatments received in the line prior to palbociclib (T-1) will be cross-tabulated with treatment line at which palbociclib was received (T), T will be crossed by treatments received at the line following palbociclib (T+1) and T+1 will be crossed by treatments received at the second line following palbociclib (T+2.)

For each of the 4 lines, whether or not that line is still ongoing or not will be described (this excludes T-1 as that line cannot be ongoing). For those not still ongoing (ie, the line has ended), the reason for ending will be described.

Time-to-event outcomes (ie, time to treatment start, time to dose reduction, treatment duration, CCI, PFS, death) will be described using the Kaplan-Meier method. In addition to reporting median event times for these measures, time-dependent event rates (eg, proportion of patients without event at various time points from a starting point of interest) will also be reported based on lifetables derived from the Kaplan-Meier analyses. All analyses will be conducted using Stata (version 14.2 or higher) statistical software and IBM SPSS Survey Reporter.

The outlined statistical methods anticipate that the selected sample is randomly drawn from normally distributed populations. However, this study will employ a convenience sample; thus, results may not be generalizable to the entire universe of patients receiving palbociclib.

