7.2.1. Definitions of Clinical Outcomes

Objective Response Rate (ORR)

Objective response rate defined as the proportion of patients achieving complete or partial response on palbociclib combination therapy.

Clinical Benefit Rate (CBR)

Clinical benefit rate is defined as the proportion of patients achieving complete or partial response, or stable disease ≥ 24 weeks on palbociclib combination therapy. Stable disease will be defined as no evidence of complete or partial response, and no progression on palbociclib therapy for 24 weeks or greater.

CCI [Redacted]

[Redacted]

Progression Free Survival (PFS)

Progression Free Survival is defined as the time from palbociclib combination treatment initiation until the earliest of (1) clinician-documented progression while on palbociclib (2) death, (3) start of a new therapy line after final palbociclib dose if the reason for discontinuation of palbociclib was disease progression, or (4) last available follow-up. Patients who did not experience a progression event (items 1, 2 and 3) will be censored at date of last available follow-up. PFS (in months) will be calculated as (first event date - palbociclib initiation date + 1)/30.4.

PFS will be analysed using a Kaplan-Meier (KM) survivor function. A table will show the survivor rate at 3 month intervals and will also show the 3 month incremental survivor rate, ie, the survivor rate from the start of that 3 month interval rather than from time zero. The median survival (if the median is reached) and a KM chart will also be shown. Time zero will be taken at the point of palbociclib initiation.

CCI [Redacted]

[Redacted]

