Number of interruptions	Primary objective 4	CRF H3b	Including zeros, ie, no interruptions
Duration of interruptions	Primary objective 4	CRF H3a	
Any cycle delays?	Primary objective 4	CRF H3b	
Duration of cycle delays	Primary objective 4	CRF H3a	
Reasons for dose change	Primary objective 4	CRF H3c	Multiple responses allowed. Reduce to patient level, ie, if “lack of response” is ticked for any dose changes then “lack of response” is considered ticked
Status of combination partner therapy when dose is changed	Primary objective 4	CRF H3d	
Time from palbociclib initiation to first dose change	Primary objective 4	CRF H3a	

Table 5. Supportive Therapies Whilst Receiving Palbociclib

Variable	Role	Data source(s)	Operational definition
All supportive therapies received whilst receiving palbociclib	Primary objective 5	CRF H4	Multiple responses allowed

Table 6. Clinical Outcomes

Variable	Role	Data source(s)	Operational definition
CCI			
Progression free survival	Exploratory objective	CRF G2e	Defined as the time from the start of palbociclib to the first subsequent progression or death. The treatment grid in section G will be used to determine in which treatment line that this occurs.
Progression free at 6, 12, 18, 24 months of treatment	Primary objective 6	CRF G2e	Proportion of patients who have not displayed progression at defined time points.
Did the patient achieve complete response whilst receiving palbociclib?	Primary objective 6	TBC	
Time to complete response	Primary objective 6	TBC	
Did the patient achieve partial response whilst receiving palbociclib?	Primary objective 6	TBC	
Time to partial response	Primary objective 6	TBC	
Objective Response Rate	Primary objective 6	CRF I1d/I1e	Proportion of patients who achieve CR/PR at CRF I1d/I1e.

Variable	Role	Data source(s)	Operational definition
Time to Death	Primary objective 6	CRF B7	This will be the time from the start of palbociclib to death. This will only include patients for whom death has been recorded.
CCI			
Survival at 12, 18, 24 months	Primary objective 6	AQ2, BQ7	Proportion of patients who have not died at defined time points.

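### The SAP's variable table limits Time to Death to patients who died, which conflicts with the Kaplan-Meier analysis of death in SAP 7.2

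*SAP*

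**What the plan says.** **SAP Appendix 1, Table 6.** Time to Death is assigned to primary objective 6 and runs from the start of palbociclib to death. The cell then adds: "This will only include patients for whom death has been recorded".

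**SAP 5.5, Clinical Outcomes, derived variables.** The same interval appears without that limit: "Time to death, defined as the time from the start of palbociclib to death".

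**SAP 7.2.** The list of time-to-event outcomes ends "PFS, death) will be described using the Kaplan-Meier method". Besides medians, the proportions without the event at various times "will also be reported based on lifetables derived from the Kaplan-Meier analyses".

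**Protocol 8.7.** The Kaplan-Meier chart "will take into account those patients for which the event has not as yet occurred".

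**SAP 7.2.1.** PFS has a censoring rule: "Patients who did not experience a progression event (items 1, 2 and 3) will be censored at date of last available follow-up". No matching rule for death is visible.

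**Survival at 12, 18, 24 months.** This separate row of Table 6 is the proportion not dead at each time point, with no limit to patients who died.

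**The concern.** Kaplan-Meier handles patients still alive at abstraction by keeping them in the risk set until they are censored. A data set of deaths only has nobody to censor, so the estimate becomes the distribution of death times given that death came before the record was abstracted. That curve falls to zero in every country. Its median is pulled down towards the length of follow-up, and its 12- and 24-month values would not agree with the fixed-time survival row of the same table.

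Two features of the plan add to the risk:

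- SAP 6 drops subjects with a missing value for an endpoint. A programmer could treat a living patient's empty death interval as missing, which would reinforce the Table 6 sentence.
- Protocol 8.1 presents direct comparison across markets as a strength of the design. Possible follow-up differs by country, so deaths-only medians would differ for that reason alone.

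**Working it through.** **Text check.** Table 6 excludes living patients. SAP 7.2 and protocol 8.7 need them, and SAP 5.5 does not exclude them. No visible sentence says which governs, or that the Table 6 sentence is only a derivation note.

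**Size.** The plan gives no figure for time to death, so there is nothing to reproduce. What follows is an illustration.

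*From the documents*
- Minimum follow-up is 3 months with fulvestrant and 6 months with an aromatase inhibitor (SAP 3).
- The core review covers about 2874 patients (SAP 2.1.1).

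*Assumed*
- Survival time T is exponential with a true median of 24, 36 or 48 months, so λ = ln 2 / median.
- Follow-up C is uniform on (a, b), where a is 3 or 6 and b is 24, 36 or 48. The upper ends are assumed, but the documents' dates make them plausible. Argentina runs from approval in December 2015 to collection completed by January 2018, about 25 months. Canada's letrozole indication runs from May 2016 to June 2019, about 37 months.

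*Formula.* For a ≤ t ≤ b, the probability of dying by t within follow-up is

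F(t) = 1 − [(b − t)e^(−λt) + (e^(−λa) − e^(−λt))/λ] / (b − a).

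The proportion with a recorded death is F(b). The deaths-only survival at t is 1 − F(t)/F(b), and the deaths-only median solves F(t) = F(b)/2.

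*Worked case: true median 24, follow-up 3–36*
- λ = 0.6931/24 = 0.02888; e^(−3λ) = 0.9170, e^(−12λ) = 0.7071, e^(−36λ) = 0.3536.
- F(36) = 1 − (0.9170 − 0.3536)/(0.02888 × 33) = 0.409.
- F(12) = 1 − [24 × 0.7071 + (0.9170 − 0.7071)/0.02888]/33 = 0.2655.
- Deaths-only survival at 12 months = 1 − 0.2655/0.4088 = 35%. The true value is 0.5^(12/24) = 71%.
- F(8.4) is about 0.204 = F(36)/2, so the deaths-only median is 8.4 months against a true 24.

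*All scenarios: deaths-only median in months*

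| Follow-up (months) | True median 24 | True median 48 |
|---|---|---|
| 3–24 | 6.1 | 6.6 |
| 3–36 | 8.4 | 9.4 |
| 3–48 | 10.3 | 12.0 |
| 6–24 | 6.5 | 7.0 |
| 6–36 | 8.7 | 9.7 |
| 6–48 | 10.5 | 12.2 |

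- Doubling true survival, with follow-up 3–36, moves the result by about 1 month (8.4 to 9.4).
- Changing only follow-up, at a true median of 36, from 3–24 to 3–48 moves it from 6.5 to 11.4.
- With follow-up 3–36, deaths-only survival is 35–40% at 12 months (true 71–84%) and 7–9% at 24 months (true 50–71%).

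*Why true survival hardly matters.* As λ tends to 0, the deaths-only density tends to P(C ≥ u)/E(C), which contains no survival parameter. For follow-up 3–36, E(C) = 19.5. The limiting median solves (36 − t)²/66 = 9.75, giving t = 36 − √643.5 = 10.6 months. However long patients live, the figure cannot pass that value.

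*Check of the remedy.* Kaplan-Meier on all patients was simulated 300 times per scenario (N = 2874, follow-up 3–36). It gave 12-month survival of 70.7%, 79.4% and 84.1% for true medians 24, 36 and 48, matching the truth. The median was 24.0 when the truth was 24.

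**Minor related point.** SAP 5.5 and Table 6 define being progression free at time t without counting death as a failure, while PFS in SAP 7.2.1 counts it. Suppose 5–10% of PFS events are deaths without documented progression (assumed), and S(t) is exponential with the protocol's cited medians. The crude proportion is then S + p(1 − S). At 24 months this gives 54–56% instead of 51% (median 24.8), and 25–29% instead of 21% (median 10.8). If deaths are censored in a lifetable instead, S^(1 − p) gives 53–55% and 23–25%.

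**The case against.** **It may be only a derivation note.** Appendix 1 lists variables and CRF sources; SAP 4.1 sets the analysis set. Time since death is collected only where it applies, so the raw interval exists only for patients who died. The appendix also splits palbociclib duration into ongoing and discontinued rows, although SAP 7.2 analyses treatment duration by Kaplan-Meier. This reading is reasonable, and under it the defect is one unclear cell. But the SAP does not say so, and a programmer working from the table would drop living patients.

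**Redacted rows may hold another survival endpoint.** They may, and this finding rests on visible text only. The conflict remains, because death itself stands unredacted in SAP 7.2 and Time to Death is the visible variable that matches it.

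**The impact is bounded.** This stands. The study is descriptive and nothing is tested. The protocol's survival objective is the proportion alive at 1 and 2 years, and the fixed-time survival row has its own definition that counts living patients.

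**Uniform follow-up overstates the bias.** This stands in part. Physicians take consecutive patients after an early index date, so follow-up may cluster at the long end. With follow-up of 24–36 months the deaths-only median is 11.8–13.4 months. That is closer to the assumed true medians of 24–48, but still far below them.

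**The progression-free point concerns a different endpoint.** This is fair: the definitions are explicit and can coexist. It is a wording matter, and the main conclusion does not depend on it.

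**Conclusion.** The concern holds and should be fixed before the all-country analysis. The Table 6 sentence cannot be reconciled with SAP 7.2 and protocol 8.7 as written, and no visible text censors living patients for death.

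If the sentence is followed, the reported median mainly measures follow-up: 6.1 to 12.2 months over the windows starting at 3 or 6 months, and up to 13.4 with follow-up of 24–36 months, against true medians of 24 to 48. The exact values rest on exponential survival, uniform follow-up and assumed upper limits. The direction does not, because removing living patients leaves a curve that must reach zero. If the sentence is only a derivation note, the numbers are safe and the SAP needs to say so. The fixed-time survival row is not affected.

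**What to change.** **Table 6, Time to Death.** Delete the sentence limiting the variable to recorded deaths. Replace it with: *All FAS patients; Kaplan-Meier from palbociclib start; patients not known to have died are censored at last available follow-up.* This mirrors the PFS rule in SAP 7.2.1. If a summary of patients who died is also wanted, give it a separate row labelled *decedents only* and keep it out of the Kaplan-Meier output.

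**Progression free at time t (minor).** In SAP 5.5 and Table 6, either refer to the Kaplan-Meier PFS rates in SAP 7.2.1, or state that deaths without progression are deliberately not counted.

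**Cost.** SAP wording only. Vital status and time since death are already abstracted (SAP 5.2), and PFS censoring already needs a last follow-up date. The CRF is not shown, so confirm that it holds that date. The Kaplan-Meier median may not be reached. In the simulations with follow-up 3–36 it was reached in 100% of runs for a true median of 24, 45% for 36 (40% in a repeat set of 300 runs) and 1% for 48. The 12- and 24-month lifetable rates remain available.
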